## 7.2      Datasets for Analysis

The following datasets will be analyzed:

- The randomized sample will include all subjects who are randomized.
- The PK sample will consist of all dosed subjects who have evaluable aripiprazole PK parameters. For analysis of the primary PK endpoint, only the completers with available values of the primary endpoints after the last scheduled injection will be included.

Protocol 031-201-00181

- The safety sample will include all randomized subjects who receive at least one dose of aripiprazole injection, regardless of any protocol violation.
- The efficacy sample will include all randomized subjects who receive at least one dose of aripiprazole injection and have at least one efficacy assessment.

### 7.3 Handling of Missing Data

No data imputation will be done for missing data in the PK analysis. The last observation carried forward (LOCF) method is used to impute missing data of the safety EPS assessment scales and efficacy assessment scales at postbaseline visits. The observed case (OC) dataset corresponding to a visit consists of data from all subjects who are evaluated at that visit. In the LOCF dataset, missing data at a postbaseline visit are imputed with the value obtained at the nearest preceding visit, except that baseline values are not carried forward to impute missing values at a postbaseline visit.

In addition, for the safety endpoints other than the EPS assessment scales, the LOCF method is also applicable for the values from the last visit for laboratory tests, vital sign parameters, ECG parameters, C-SSRS suicidality-related parameters, VAS for Subject-reported Rating of Pain at Most Recent Injection Site, and Investigator's Assessment of Most Recent Injection Site.

### 7.4 Primary and Secondary Endpoint Analyses

#### 7.4.1 Primary Endpoint Analyses

Safety assessments including AEs, vital signs, ECGs, clinical laboratory monitoring (serum chemistry, hematology, and urinalysis), physical examinations, EPS (SAS, AIMS, and BARS), VAS scores for pain perception, Investigator's Assessment of Most Recent Injection Site, and suicidality via the C-SSRS will be summarized for the safety sample by treatment group. The mean change from baseline will be provided for vital signs, ECGs, clinical laboratory, and EPS assessments by visit, treatment group, and disease type. The incidence of clinically relevant abnormalities in vital signs, ECGs, and clinical laboratory results will be summarized descriptively by visit, treatment group, and disease type.

Plasma concentrations of aripiprazole will be analyzed using noncompartmental methods. The following PK parameters will be estimated and summarized descriptively for aripiprazole:  $C_{56}$  and  $AUC_{0-56}$  of aripiprazole 2M LAI 960 mg after the fourth dose,  $C_{28}$  of aripiprazole IM depot 400 mg after the eighth dose, and  $AUC_{0-28}$  of aripiprazole IM depot 400 mg after the seventh and eighth doses over the course of 32 weeks. The 90%

Protocol 031-201-00181

CI of GMR of  $C_{56}$  of aripiprazole after the fourth injection of aripiprazole 2M LAI 960 mg (test) to  $C_{28}$  after the eighth injection of aripiprazole IM depot 400 mg (reference) will be provided. An analysis of variance will be performed on the natural-log transformed PK parameters using the MIXED procedure in the Statistical Analysis System (SAS). The mixed-effects linear model will include treatment group, disease type (if applicable), and PK sampling schedule as fixed effects and subject as a random effect. The least squares means for the 2 treatment groups, their difference, and the 90% CI for their difference will be derived. The antilog of the confidence limits will provide the 90% CI for the GMR of the 2 treatments. For subjects enrolled to the robust sampling schedule, the values of  $AUC_{0-28}$  after seventh and eighth doses of aripiprazole IM depot 400 mg (reference) will be summed up before analyzing by the same method together with  $AUC_{0-56}$  after the fourth injection of aripiprazole 2M LAI 960 mg (test). Only subjects who receive a fourth dose of aripiprazole 2M LAI 960 mg or a seventh and/or eighth dose of aripiprazole IM depot 400 mg and have  $C_{56}$ ,  $C_{28}$ ,  $AUC_{0-28}$ , and  $AUC_{0-56}$  values determined for the respective treatments will be included in the analysis.

#### 7.4.2 Secondary Endpoint Analyses

Individual and summary tables, using descriptive statistics (N, median, mean, SD, CV, minimum, maximum) will be provided for the following aripiprazole PK endpoints:

- $C_{max}$  and  $t_{max}$  after the first and fourth doses of aripiprazole 2M LAI 960 mg
- $AUC_{0-56}$  and  $C_{56}$  after the first dose of aripiprazole 2M LAI 960 mg
- $AUC_{0-28}$  and  $AUC_{29-56}$  after the fourth dose of aripiprazole 2M LAI 960 mg
- PTF% after the fourth dose of aripiprazole 2M LAI 960 mg (for aripiprazole only)
- $C_{max}$  and  $t_{max}$  after the first, seventh, and eighth doses of aripiprazole IM depot 400 mg
- $AUC_{0-28}$  and  $C_{28}$  after the first dose of aripiprazole IM depot 400 mg
- PTF% after the eighth dose of aripiprazole IM depot 400 mg (for aripiprazole only)
- $C_7$  and  $C_{14}$  after the first injection of aripiprazole 2M LAI 960 mg and aripiprazole IM depot 400 mg from subjects enrolled to the robust sampling schedule.

Values for  $C_{max}$ ,  $AUC$ ,  $t_{max}$ , and PTF% will be summarized based on samples from subjects enrolled to the robust sampling schedule; whereas  $C_{28}$  and  $C_{56}$  after the first injection will be summarized based on samples from subjects enrolled to the robust and sparse sampling schedules.

Protocol 031-201-00181

Efficacy assessments including the PANSS (schizophrenia subjects only), CGI-S, CGI-I, SWN-S, MADRS (bipolar subjects only), YMRS (bipolar subjects only), and CGI-BP (bipolar subjects only) will be summarized for the efficacy sample at each visit by treatment group and disease type, if applicable. These analyses will be performed for both LOCF and OC data. In addition, the linear mixed-effects model will be used to explore the effect of the treatment and change from baseline over time, as applicable.

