### 1.3 Pharmacokinetics

Abilify Maintena activity is presumably primarily due to the parent drug, aripiprazole, and to a lesser extent, to its major metabolite, dehydro-aripiprazole, which has been

Protocol 031-201-00181

shown to have affinities for D2 receptors similar to the parent drug and represents about 29% of the parent drug exposure in plasma.

The plasma aripiprazole concentrations after single- and multiple-dose administration of Abilify Maintena are well established. The aripiprazole 2-month RTU formulation at the 960 mg dose is expected to provide plasma concentrations of aripiprazole within the concentration range of Abilify Maintena.

Aripiprazole absorption into the systemic circulation is slow and prolonged following Abilify Maintena administration due to low solubility of aripiprazole particles. The average absorption half-life of aripiprazole from Abilify Maintena is 28 days. The absorption of aripiprazole from Abilify Maintena was complete relative to the IM standard (immediate-release) formulation. The dose-adjusted Cmax values for the depot formulation were approximately 5% of Cmax from the IM standard formulation. Following a single-dose administration of Abilify Maintena in the deltoid and gluteal muscle, the extent of absorption (area under the concentration-time curve [AUC]) was similar for both injection sites, but the rate of absorption (Cmax) was higher following administration to the deltoid muscle.

Based on results from trials with oral administration of aripiprazole, aripiprazole is widely distributed throughout the body with an apparent volume of distribution of 4.9 l/kg, indicating extensive extravascular distribution. At therapeutic concentrations, aripiprazole and dehydro-aripiprazole are greater than 99% bound to serum proteins, binding primarily to albumin.

Elimination of aripiprazole is mainly through hepatic metabolism involving 2 cytochrome P450 (CYP) isozymes, CYP2D6 and CYP3A4. Aripiprazole is not a substrate of CYP1A1, CYP1A2, CYP2A6, CYP2B6, CYP2C8, CYP2C9, CYP2C19, or CYP2E1 enzymes. Aripiprazole also does not undergo direct glucuronidation.

Following a single oral dose of [C]-labeled aripiprazole, approximately 27% of the administered radioactivity was recovered in the urine and approximately 60% in the feces. Less than 1% of unchanged aripiprazole was excreted in the urine and approximately 18% was recovered unchanged in the feces.

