### 3.2.3 Oral Overlap

At the time of administration of the first dose of IMP, subjects will begin a 7- to 14-day period (oral overlap) where they will transition from their current oral antipsychotic to include injections of IMP, according to the scenarios described in [Table 3.2.3-1](#).

Subjects currently stabilized on a non-aripiprazole oral antipsychotic who are enrolled to a sparse sampling schedule will continue on their medication and subjects who are enrolled to a robust sampling schedule will switch to 10 to 20 mg oral aripiprazole (dose determined by the investigator). Subjects will take their oral antipsychotic medications concurrently with IMP for 7 days after the first administration of aripiprazole 2M LAI 960 mg or 14 days after the first administration of aripiprazole IM depot 400 mg. The oral antipsychotic will be discontinued after 7 days of administration of aripiprazole 2M LAI 960 mg and after 14 days of administration of aripiprazole IM depot 400 mg.

For subjects currently stabilized on oral aripiprazole, the recommended supplemental oral aripiprazole dose will be reduced to 10 mg/day with the first dose of IMP for subjects with a previous dose of 10 to 20 mg/day or to 15 mg/day for subjects with a previous dose of > 20 to 30 mg/day ([Table 3.2.3-2](#)).

There will be no oral overlap for subjects who are taking Abilify Maintena® as their current antipsychotic medication. Subjects who are on Abilify Maintena as their current antipsychotic cannot be enrolled until their next scheduled dose is required as specified in the label, and they cannot receive IMP any earlier than 26 days after the last Abilify Maintena injection. In this scenario, the investigator should carefully consider the screening period and the timing of randomization in relation to the first dose of IMP and previous dose of Abilify Maintena.

Given the addition of a second antipsychotic, investigators should consider reducing the dose of the current oral antipsychotic, mood stabilizer, or antidepressant medications to the mid to lower range of the recommended dose range described in the labeling.

Aripiprazole tablets for oral overlap will be provided from a commercial supply.

Protocol 031-201-00181

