**Table 3.2.3-1 Scenarios for Initiation of Oral Aripiprazole Overlap During the First 2 Weeks After the Initiation of IMP**

| Treatment                           | PK Sampling Schedule      | Current Antipsychotic Medication a  |  |  |
|-------------------------------------|---------------------------|--|--|--|
|                                     |                           | Abilify Maintena b
300 or 400 mg | Oral Aripiprazole c         | Non-aripiprazole Oral Antipsychotic                            |
| Aripiprazole 2M LAI 960 mg   | Sparse             | No oral overlap                                | 7-day oral overlap with adjusted dose  | Continue current antipsychotic for 7 days                      |
|                                     | Robustd | Not applicable                                 | Not applicable                         | (Switch to) Oral aripiprazole 10 to 20 mg: 7-day oral overlap  |
| Aripiprazole IM depot 400 mg | Sparse             | No oral overlap                                | 14-day oral overlap with adjusted dose | Continue current antipsychotic for 14 days                     |
|                                     | Robustd | Not applicable                                 | Not applicable                         | (Switch to) Oral aripiprazole 10 to 20 mg: 14-day oral overlap |

aSubjects with bipolar I disorder who are taking a mood stabilizer will be permitted to stay on their mood stabilizer over the course of the trial, and if taking an antidepressant, to continue treatment with their antidepressant unless it is unless the medication is prohibited during the trial (eg, fluoxetine, fluoxetine/olanzapine; [Table 4.1-1](#)).

bSubjects on an LAI other than Abilify Maintena are excluded from the trial. Subjects on Abilify Maintena as their current antipsychotic medication cannot enroll to the robust sampling schedule.

cFor subjects who are taking oral aripiprazole 10 to 20 mg as their current antipsychotic, the dose will be reduced for the overlap period ([Table 3.2.3-2](#)).

dIn order to be enrolled to the robust sampling schedule, subjects must have demonstrated prior tolerability to aripiprazole, must be stabilized on an existing non-aripiprazole antipsychotic, and must switch to oral aripiprazole on Day 1 for 7 or 14 days depending on the assigned IMP treatment.

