| 7.                                      | Subjects must be clinically stable (based on investigator judgment, subject/caregiver report, and/or documentation) for at least 2 months prior to screening AND 
 
On a stable dose of 1 of the following oral atypical antipsychotic medication for at least 2 months prior to screening: aripiprazole (sparse only), brexpiprazole, risperidone, olanzapine, quetiapine, paliperidone, cariprazine, lurasidone, ziprasidone, or asenapine; or Abilify Maintena (sparse only). Additionally, subjects with bipolar I disorder who are stabilized on their current medications for at least 2 months prior to screening may continue their mood stabilizer (lithium, valproic acid, lamotrigine) and antidepressant (citalopram, escitalopram, sertraline).
 
Other oral non-aripiprazole, antipsychotic medications may be allowed if approved by the medical monitor and sponsor; however, clozapine will not be allowed. (Subjects intended to enroll to the robust sites may not be taking oral aripiprazole or Abilify Maintena as their current atypical antipsychotic.)
 
 |
| 8.                                      | Able to understand the nature of trial and follow protocol requirements and procedures.   |

AEs = adverse events; ECG = electrocardiogram.

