| 5.  | Subjects enrolled to the robust sampling schedule must not have taken oral aripiprazole for 30 days or Abilify Maintena for 1 year, prior to screening.  |
| 6.  | Females who are pregnant, breast-feeding, lactating, and/or have a positive pregnancy test result prior to receiving IMP. A negative serum pregnancy test must be confirmed prior to the first dose of IMP for all female subjects.  |
| 7.  | Subjects who participated in any clinical trial involving an oral psychotropic medication within 1 month prior to the administration of IMP, as well as subjects who participated in a clinical trial with an aripiprazole depot-containing formulation of a psychotropic medication within the last 1 year or a non-aripiprazole depot formulation within the last 6 months.  |
| 8.  | Any major surgery within 30 days prior to enrollment or scheduled/elective surgery during the trial.   |
| 9.  | Evidence of organ dysfunction or any clinically significant deviation from normal in the physical, electrocardiographic, or clinical laboratory examinations.  |
| 10. | Subjects who have a significant risk of committing suicide based on history, routine psychiatric status examination, investigator's judgment, or who have an answer of "yes" on questions 4 or 5 (current or over the last 6 months) on the baseline version of the C-SSRS.  |
| 11. | Subjects currently in an acute relapse of schizophrenia.   |
| 12. | Subjects with a current DSM-5 diagnosis other than schizophrenia or bipolar I disorder, including schizoaffective disorder, major depressive disorder, delirium, dementia, amnestic, or other cognitive disorders. Also, subjects with borderline, paranoid, histrionic, or antisocial personality disorder.   |
| 13. | Subjects who are considered treatment-resistant to an atypical antipsychotic medication (subjects need to have shown a previous response to an antipsychotic medication other than clozapine).   |
| 14. | Subjects with a history of neuroleptic malignant syndrome or clinically significant tardive dyskinesia as assessed by the investigator.  |
| 15. | Any other sound medical reason as determined by the clinical investigator.   |

Protocol 031-201-00181

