## 6.3 Secondary Pharmacokinetics Variables

The following secondary PK parameters are estimated for aripiprazole after the administration of aripiprazole 2M LAI 960 mg and aripiprazole IM depot 400 mg:

- $C_{max}$  and  $t_{max}$  after the first and fourth doses of aripiprazole 2M LAI 960 mg;
- $AUC_{0-56}$  and  $C_{56}$  after the first dose of aripiprazole 2M LAI 960 mg;
- $AUC_{0-28}$  and  $AUC_{29-56}$  after the fourth dose of aripiprazole 2M LAI 960 mg;
- Peak-to-trough percent fluctuation (PTF%) after the fourth dose of aripiprazole 2M LAI 960 mg;
- $C_{max}$  and  $t_{max}$  after the first, seventh and eighth doses of aripiprazole IM depot 400 mg;
- $AUC_{0-28}$  and  $C_{28}$  after the first dose of aripiprazole IM depot 400 mg;
- PTF% after the eighth dose of aripiprazole IM depot 400 mg.

$C_{max}$ ,  $t_{max}$ , AUC, and PTF% are determined only from subjects enrolled to the robust sampling schedule;  $C_{56}$  and  $C_{28}$  are determined from subjects enrolled to the sparse and robust sampling schedule.

The following PK parameters are estimated for aripiprazole after administration of aripiprazole 2M LAI 960 mg + oral aripiprazole 10 to 20 mg for 7 days and aripiprazole IM depot 400 mg + oral aripiprazole 10 to 20 mg for 14 days (this endpoint is only for subjects enrolled to the robust sampling schedule):

- Plasma concentration of aripiprazole 7 days postdose ( $C_7$ )
- Plasma concentration of aripiprazole 14 days postdose ( $C_{14}$ ).

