## 10.2 Secondary Pharmacokinetics Endpoint Analyses

Individual and summary tables, using descriptive statistics (N, median, mean, standard deviation, coefficient of variation, minimum, maximum) will be provided for the following aripiprazole PK endpoints,

- $C_{max}$  and  $t_{max}$  after the first and fourth doses of aripiprazole 2M LAI 960 mg,
- $AUC_{0-56}$  and  $C_{56}$  after the first dose of aripiprazole 2M LAI 960 mg,
- $AUC_{0-28}$  and  $AUC_{29-56}$  after the fourth dose of aripiprazole 2M LAI 960 mg,
- PTF% after the fourth dose of aripiprazole 2M LAI 960 mg (for aripiprazole only),
- $C_{max}$  and  $t_{max}$  after the first, seventh and eighth doses of aripiprazole IM depot 400 mg,
- $AUC_{0-28}$  and  $C_{28}$  after the first dose of aripiprazole IM depot 400 mg,
- PTF% after the eighth dose of aripiprazole IM depot 400 mg (for aripiprazole only),

Protocol 031-201-00181

- $C_7$  and  $C_{14}$  after the first injection of aripiprazole 2M LAI 960 mg and aripiprazole IM depot 400 mg from subjects enrolled to the robust sampling schedule.

Values for  $C_{max}$ , AUC,  $t_{max}$ , and PTF% will be summarized based on samples from subjects enrolled to the robust sampling schedule; whereas  $C_{28}$  and  $C_{56}$  will be summarized based on samples from subjects enrolled to the robust and sparse sampling schedules.

[REDACTED]

Protocol 031-201-00181

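### First-dose C28 and C56 pool in sparse subjects who may have had Abilify Maintena only 26 days earlier, so values labelled as first-dose can contain depot carry-over

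*Protocol*

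**What the plan says.** C28 after the first 400 mg dose and C56 after the first 960 mg dose are named secondary endpoints (Protocol 3.5.2.1, SAP 6.3). Protocol 7.4.2 states that these values "after the first injection will be summarized based on samples from subjects enrolled to the robust and sparse sampling schedules". SAP 6.3 says that C56 and C28 "are determined from subjects enrolled to the sparse and robust sampling schedule", and SAP 10.2 that they "will be summarized based on samples from subjects enrolled to the robust and sparse sampling schedules".

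The two schedules have different rules on earlier aripiprazole:

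- **Sparse.** Inclusion criterion 7 admits subjects on Abilify Maintena to the sparse schedule only, after at least 2 months of stable use. Table 3.2.3-1 lists 300 or 400 mg. Under Protocol 3.2.3 their next injection must be due, and "they cannot receive IMP any earlier than 26 days after the last Abilify Maintena injection".
- **Robust.** "Subjects on Abilify Maintena as their current antipsychotic medication cannot enroll to the robust sampling schedule" (Table 3.2.3-1, footnote b). Under exclusion criterion 5, robust subjects "must not have taken oral aripiprazole for 30 days or Abilify Maintena for 1 year, prior to screening".

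First-dose Cmax, tmax, AUC, C7 and C14 come from robust subjects only. The PK sample is every dosed subject with evaluable parameters (Protocol 7.2, SAP 5). Randomisation is stratified by sampling schedule and disease type, not by earlier depot use.

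**The concern.** A gap of 26 days is about one dosing interval, not a washout. Protocol 2.2 identifies the reference arm as Abilify Maintena itself, so for a Maintena entrant randomised to 400 mg the first trial dose is in effect the next maintenance dose. The Day 29 trough then contains the new injection plus what remains of the earlier ones. In the 960 mg arm the same happens at Day 57, to a smaller degree.

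The protocol protects the other first-dose parameters from this by taking them from robust subjects with a one-year Maintena-free period. Only the first-dose troughs lack that protection, yet they are reported beside the others.

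At stake is an upward shift in two descriptive summaries that grows with the number of Maintena entrants. The shift is larger for the reference (C28) than for the test product (C56), so a reader who compares first-dose troughs across arms would also be misled.

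**Working it through.** The documents give no target figure for these summaries, so there is nothing to reproduce. The check estimates the carry-over by superposition.

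**Inputs**
- Half-life *h*: 24 days, the median after 400 mg Abilify Maintena (Protocol 1.3). The range is 20 days (the mean after 1200 mg of the LAI, same section) to 28 days ("The average absorption half-life of aripiprazole from Abilify Maintena is 28 days").
- Earlier injections every 28 days, the last one 28 days before Day 1 (assumed; 26 is the minimum).
- Mono-exponential decline (assumed).
- Enrolment: 182 sparse subjects out of 258 (Protocol 3.1).

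**Fraction left after 28 days:** r = 2^(−28/h). **After 56 days:** r².

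**Inflation per Maintena entrant, relative to a value without earlier depot**

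| Case | Formula | h = 20 | h = 24 | h = 28 |
|---|---|---|---|---|
| r | 2^(−28/h) | 0.379 | 0.445 | 0.500 |
| r² | | 0.144 | 0.198 | 0.250 |
| C28, steady state on 400 mg | 1 + r/(1−r) | 1.61 | 1.80 | 2.00 |
| C28, two earlier 300 mg injections | 1 + 0.75(r + r²) | 1.39 | 1.48 | 1.56 |
| C56, steady state, equal steady-state troughs in both arms | 1 + r²/(1−r²) | 1.17 | 1.25 | 1.33 |
| C56, steady state, concentration proportional to dose | 1 + (400/960)·r/(1−r) | 1.25 | 1.33 | 1.42 |
| C56, two earlier 300 mg injections, equal troughs | 1 + 0.75r² | 1.11 | 1.15 | 1.19 |
| C56, two earlier 300 mg injections, dose-proportional | 1 + (300/960)(r + r²) | 1.16 | 1.20 | 1.23 |

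The equal-troughs rows use the geometric mean ratio of 1.0 assumed in Protocol 7.1. Two earlier 300 mg injections serve as the floor because at least 2 months of stable use is required.

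**Effect on the pooled mean** = share of the pool × (ratio − 1). The share is not stated, so these figures are illustrative.
- At 10% of the pool (0.10 × 258 = 25.8 subjects; 25.8/182 = 14.2% of sparse subjects): C28 rises by 0.10 × 0.80 = 8%, range 4% (ratio 1.39) to 10% (ratio 2.00). C56 rises by 0.10 × 0.25 = 2.5%, range 1% (1.11) to 4% (1.42).
- At 10%, 25% or 50% of sparse subjects, the pool share is that figure × 182/258 = 7.1%, 17.6% or 35.3%. With h = 24, C28 rises by about 6%, 14% or 28%, and C56 (equal troughs) by about 2%, 4% or 9%.

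**Primary endpoints.** At Day 225 the fraction of the Day 1 trough left is 2^(−224/h) = 0.04% to 0.4%, which is negligible.

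**Oral aripiprazole.** Overlap in the 400 mg arm stops 14 days after the first injection, leaving 14 days to the C28 sample. With CL 3.71 L/h and V 4.9 L/kg (Protocol 1.3) and an assumed 70 kg, the half-life is 0.693 × 343/(3.71 × 24) = 2.7 days, so about 3% of the oral contribution remains. With the 1.88 L/h quoted for CYP2D6 poor metabolisers, the half-life is 5.3 days and about 16% remains. Robust subjects take oral overlap too, so this is not peculiar to sparse entrants. In the 960 mg arm oral dosing ends about 7 weeks before C56, and the contribution is negligible.

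**The case against.** The facts of the pooling are not in dispute. The case against acting has five parts.

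- **No inference rests on these tables.** They are descriptive, with no test, interval or margin. This stands, and it limits the weight of the point.
- **The label may be literally true.** The value does follow the first trial injection, and the objective is only to determine the PK of aripiprazole. But these values sit beside first-dose parameters from subjects with a one-year depot-free period, and a reader will take them as first-dose troughs. For Maintena entrants on 400 mg they are closer to maintenance troughs.
- **Carry-over is visible by subject.** A Day 1 predose sample is taken, earlier medication is recorded, individual tables are promised, and the median is less sensitive than the mean. All true, but no stated analysis uses this information to separate these subjects.
- **The size is soft.** The entrant share is unknown. At 10% of the pool, the 2.5% shift in C56 is below a standard error of about 4% (46%/√129, if the planning CV applied to first-dose values and all 129 per arm contributed). Protocol 1.3 reports a late tmax and a secondary peak for the LAI, which fit a mono-exponential tail poorly. A one-compartment calculation with a 28-day absorption half-life gives 2.00 and 1.42, but it only repeats the h = 28 case and is not independent support. The pooled figures are therefore illustrations. The direction is not in doubt, and unlike sampling error the shift does not shrink with more subjects.
- **The populations would still differ after a split.** Sparse subjects on other antipsychotics take no oral aripiprazole, whereas robust subjects do. This stands. The split removes depot carry-over but does not make the two schedules identical.

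Parts of the SAP are redacted after section 10.2 and after Appendix 3, and might address the matter. Protocol 7.4.2 is readable and does not.

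**Conclusion.** The concern holds on the readable text. Following the stated rule mixes true first-dose troughs with troughs that carry residual depot drug. With a 24-day half-life and steady state on 400 mg, each Maintena entrant's C28 is about 1.8 times (1.6 to 2.0), and C56 about 1.25 to 1.33 times (1.17 to 1.42), the value without earlier depot. The floor of two earlier 300 mg injections still gives about 1.5 for C28 and 1.11 to 1.23 for C56. These ratios rest on superposition and mono-exponential decline; the effect on the pooled means also depends on an entrant share that the documents do not give. The consequence is confined to descriptive secondary endpoints. It is worth correcting because it is directional and cheap to fix, not because it threatens the trial's conclusions.

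**What to change.** In Protocol 7.4.2 and SAP 6.3 and 10.2, state that first-dose C28 and C56 are summarised, over both schedules, in subjects whose recorded antipsychotic at entry was not Abilify Maintena, and that Maintena entrants are presented separately by treatment group. Identify them from the recorded medication, not from a cut-off on the Day 1 predose concentration. Subjects who enter on oral aripiprazole can stay in the main table.

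The cost is a wording change in both documents; the protocol change goes through the amendment policy in section 13. No new data are needed, because current medication, including Abilify Maintena, is already recorded at screening and on Day 1 (Tables 3.7.3-1 and 3.7.3-2). The main table will have fewer subjects, but none is lost from reporting. Adding a split only in the SAP beside the pooled table would be lighter and would expose the effect, but it would leave carry-over in the main summary.
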